#### 9.4.2. Tertiary Endpoints

Tertiary efficacy endpoints include the following. Note that analysis will be performed for each protocol-scheduled time point for each analysis variable and method, but the focus will be on the Week 24 time point.

- Change from Baseline on UPDRS-5 at Week 24
  - MMRM on observed data (also on UPDRS subgroups)
  - Wilcoxon Rank test on observed data
- Change from Baseline on ADAS-Cog 13 at Week 24
  - MMRM on observed data
  - Wilcoxon Rank test on observed data
- Change from Baseline in the Total score, and the Basic, Instrumental, Independence subscores of the ADCS-ADL scale at Week 24
  - MMRM on observed data (also on Concomitant Parkinsonian Meds subgroups)
  - Wilcoxon Rank test on observed data
- Change from Baseline in the Total Composite z-score and in the actual score (NOT the z-scores) of each individual domain of the CDR computerized assessment system at Week 24. Thus, in addition to the Total Composite, this includes the following 7 domains:

Power of Attention
Continuity of Attention
Cognitive Reaction Time
Response Variability
Quality of Working Memory
Quality of Episodic Secondary Memory
Speed of Memory

- MMRM on observed data
- Wilcoxon Rank test on observed data
- Change from Baseline in COWAT total score at Week 24

- MMRM on observed data
- Wilcoxon Rank test on observed data
- Change from Baseline in a composite z-score of the 7 CDR System domains plus the COWAT total score at Week 24
  - MMRM on observed data
  - Wilcoxon Rank test on observed data
- Change from Baseline in the sum of Parts A and B (Delusions and Hallucinations), and the sum of Parts of D and E (Depression and Anxiety) of the NPI at Week 24
  - MMRM on observed data
  - Wilcoxon Rank test on observed data
- Change from Baseline on the total severity score and distress score of the NEVHI score at Week 24 for subjects with visual hallucinations
  - MMRM on observed data
  - Wilcoxon Rank test on observed data
- Number (%) of patients with shifts from baseline in the NEVHI Total Severity Score and in the Distress Score (ie, 2 separate analyses) at Week 24, using a CMH row means score (CHM RMS) test. The categories for shifts are ordered as:
  - worsening from baseline
  - remaining unchanged from baseline
  - improving from baseline.

*Sample* SAS code for the CMH RMS is as follows (where MMSEbase is the baseline randomization stratum level for the patient, NOT the actual MMSE value):

```
Proc freq data=dat;  
    Tables MMSEbase*treat*outcome / cmh rms;  
Run;
```

- Change from Baseline in CAF severity score for each question (there are 2 questions) at Week 24. Note that patients with no cognition or confusion scores are assigned a 0 and thus are included in this analysis.
  - MMRM on observed data
  - Wilcoxon Rank test on observed data
- The number (%) of patients with CAF cognition or confusion (ie, a yes on one or the other question) at Week 24. This will be generated separately for each of the 2 questions as well as ‘overall’, ie, having a YES on either question.
  - CMH test for general association (similar SAS code as for the CMH RMS but the RMS option is not needed).

- Change from Baseline on DS Total Score at Week 24
  - MMRM on observed data
  - Wilcoxon Rank test on observed data

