
 
To assess the effects of RVT-101 versus placebo on cognitive function as measured by a composite z-score combining the 7 domains for the CDR computerized assessment system and the COWAT after 24 weeks of treatment
 
	Change from Baseline in composite z-score combining the 7 CDR System domains plus the COWAT at Week 24

 
To assess the effects of RVT-101 versus placebo on hallucinations and delusions as measured by a 2-item subscore on the NPI which is the sum of the scores for the hallucinations and delusions domains (Parts A and B) after 24 weeks of treatment
 
	Change from Baseline in the sum of Parts A and B of the NPI at Week 24

 
To assess the effects of RVT-101 versus placebo on visual hallucinations as measured by the NEVHI after 24 weeks of treatment
 
	Change from Baseline on the total severity score and distress score of the NEVHI score at Week 24 for subjects with visual hallucinations

 
To assess the effects of RVT-101 versus placebo on fluctuations in cognition using the CAF after 24 weeks of treatment
 
	Change from Baseline in CAF severity score at Week 24 for subjects with cognitive fluctuations

 
To assess the effects of RVT-101 versus placebo on subject dependence using the DS after 24 weeks of treatment
 
	Change from Baseline on DS at Week 24
Safety	

 
To assess the safety and tolerability of RVT-101 after 24 weeks of treatment
 
	AEs, physical examinations, vital signs (including orthostatic changes in BP and HR), ECGs, routine clinical laboratory assessments, questionnaire for symptoms potentially associated with orthostasis, and C-SSRS.
Exploratory	

 
To assess the effects of RVT-101 versus placebo on quality of life as measured by the EQ-5D-5L after 24 weeks of treatment
 
	Change from Baseline on EQ-5D-5L at Week 24

 
To assess the effects of RVT-101 versus placebo on sleep-related behaviors as measured by the modified CSI
 
	Change from Baseline on CSI scores (Part I, Part II) at Week 24

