#### **10.4.3. Tertiary Efficacy Analyses**

Other cognition and functional efficacy endpoints include:

- Change from Baseline on UPDRS-5 at Week 24
- Change from Baseline in the ADCS-ADL at Week 24
- Change from Baseline in the Basic and Instrumental subscales of the ADCS-ADL at Week 24
- Change from Baseline in ADAS-Cog-13 at Week 24
- Change from Baseline in the Total Composite z-score and in the actual score (NOT the z-scores) of each individual domain of the CDR computerized assessment system at Week 24. Thus, in addition to the Total Composite, this includes the following 7 domains:

Power of Attention
--------------------

Continuity of Attention
Cognitive Reaction Time
Response Variability
Quality of Working Memory
Quality of Episodic Secondary Memory
Speed of Memory

- Change from Baseline in COWAT score at Week 24
- Change from Baseline in composite z-score combining the 7 CDR System domains with the COWAT
- Change from Baseline in the sum of Parts A & B of the NPI at Week 24
- Change from Baseline in the total severity score and the distress score on the NEVHI at Week 24 for subjects with visual hallucinations
- Number (%) of patients with shifts from baseline in the NEVHI Total Severity Score and in the Distress Score (ie, 2 separate analyses) at Week 24
- Change from Baseline in CAF severity score for each question (there are 2 questions) at Week 24
- The number (%) of patients with CAF cognition or confusion (ie, a yes on one or the other question) at Week 24.
- Change from Baseline in DS at Week 24

Comparisons of RVT-101 versus placebo for most of the above endpoints will be performed using MMRM similar to the models described for the primary endpoints based on change from baseline at Week 24. CMH tests will be used on shifts from baseline in the NEVHI total severity score and number (%) of patients with CAF cognition or confusion.

Details and additional sensitivity analyses will be described in the SAP.

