
 
To assess the effects of Intepirdine versus placebo on working memory as a measure of executive function as assessed by the COWAT after 24 weeks of treatment
 
	Change from Baseline in COWAT score at Week 24

 
To assess the effects of Intepirdine versus placebo on cognitive function as measured by a composite z-score combining the 7 domains for the CDR computerized assessment system and the COWAT after 24 weeks of treatment
 
	Change from Baseline in composite z-score combining the 7 CDR System domains plus the COWAT at Week 24

 
To assess the effects of Intepirdine versus placebo on hallucinations and delusions as measured by a 2-item subscore on the NPI which is the sum of the scores for the hallucinations and delusions domains (Parts A and B) after 24 weeks of treatment
 
	Change from Baseline in the sum of Parts A and B of the NPI at Week 24

 
To assess the effects of Intepirdine versus placebo on visual hallucinations as measured by the NEVHI after 24 weeks of treatment
 
	Change from Baseline on the total severity score and distress score of the NEVHI score at Week 24 for subjects with visual hallucinations

 
To assess the effects of Intepirdine versus placebo on fluctuations in cognition and on confusion using the CAF after 24 weeks of treatment
 
	Change from Baseline in CAF severity scores at Week 24 for subjects with cognitive fluctuations

 
To assess the effects of Intepirdine versus placebo on subject dependence using the DS after 24 weeks of treatment
 
	Change from Baseline on DS at Week 24

 
To assess the safety and tolerability of Intepirdine after 24 weeks of treatment
 
	AEs, physical examinations, vital signs (including orthostatic changes in BP and HR), ECGs, routine clinical laboratory assessments, questionnaire for symptoms potentially associated with orthostasis, and C-SSRS.
Exploratory	

 
To assess the effects of Intepirdine versus placebo on quality of life as measured by the EQ-5D-5L after 24 weeks of treatment
 
	Change from Baseline on EQ-5D-5L at Week 24

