### 5.8. Clinician Assessment of Fluctuation (CAF)

The CAF assesses fluctuating cognition and impaired consciousness over the previous month (Walker 2000). The CAF is one of the measures of cognitive fluctuation recommended by the DLB Consortium when applying the DLB diagnostic criteria (McKeith 2005).

The CAF is a 2-item questionnaire that asks about fluctuating cognition and fluctuation confusion, with each question reported as Yes, No, and Not Known.

- **Fluctuating Cognition:** Does the patient ever have spontaneous impaired alertness and concentration, ie, appear drowsy but awake, look dazed, not be aware of what is going on around? (Clear examples demonstrating impaired consciousness with variations in performance/cognition are required to receive a positive rating.) Have these episodes occurred within the last month?
- **Fluctuation Confusion:** Has the level of confusion experienced by the patient tended to vary a lot recently from day to day or week to week? Has it become worse, then improved for a while, ie, been up and down? (Significant fluctuation is regarded as present if distinct examples of differences in performance/cognition can be given on at least two occasions over the past month.)

If fluctuation is reported as ‘yes’, frequency (Table 10) and duration (Table 11) scores are assessed. These scores (frequency and duration) are multiplied to achieve a severity score (Van Dyk 2015).

- If the clinician assessment of fluctuation is that the patient does not have fluctuation, the patient is assigned a severity score of 0 for that question.

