**Table 11: Duration of Fluctuating Cognition or Confusion Scores (Study RVT-101-2001)**

Duration of fluctuating Cognition or Confusion	
0	seconds
1	< 5 minutes
2	5 minutes – 1 hour
3	> 1 hour
4	> 1 Day

If either frequency or duration is missing for either question, the severity score is set to missing.

These data will be analyzed as follows for each question separately, by visit:

- The number (%) of patients with cognition (or confusion) will be tabulated..
- For each question, changes over time in severity scores.
- The number (%) of patients with EITHER a ‘yes’ on cognition OR a ‘yes’ on confusion (or a YES on both) vs those with a ‘no’ on BOTH.

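### The CAF severity endpoint is defined for subjects who fluctuate, but SAP 9.4.2 analyses all subjects and no planned output gives the change in the named group

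*SAP*

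**What the plan says.** The endpoint column of protocol section 4 reads "Change from Baseline in CAF severity score at Week 24 for subjects with cognitive fluctuations". SAP Table 3 repeats it almost word for word: "Change from Baseline in CAF severity scores at Week 24 for subjects with cognitive fluctuations".

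The objective beside each endpoint carries no such limit. The protocol asks for the effect "on fluctuations in cognition using the CAF after 24 weeks of treatment", and the SAP for the effect "on fluctuations in cognition and on confusion using the CAF after 24 weeks of treatment".

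The analysis sections are also unrestricted. Protocol 10.4.3 lists "Change from Baseline in CAF severity score for each question (there are 2 questions) at Week 24". In SAP 5.8, when the clinician finds no fluctuation, "the patient is assigned a severity score of 0 for that question". SAP 9.4.2 then says of the severity analysis: "Note that patients with no cognition or confusion scores are assigned a 0 and thus are included in this analysis". By SAP 7.4 and 9.1 the population is ITT.

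A zero stands for an assessed absence of fluctuation, not for missing data: "If either frequency or duration is missing for either question, the severity score is set to missing".

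**The concern.** Fluctuating cognition is one of three core diagnostic features in inclusion criterion 1 (protocol 6.2). A subject can enter on the other two, or on one of them plus a suggestive feature, so some randomised subjects may have no fluctuation at Baseline. Such a subject starts at 0, the best possible score, and can only stay there or get worse. SAP 9.4.2 averages these subjects with those who have the symptom.

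At stake is what the reported number means. Someone who reads SAP Table 3 and then the CAF severity result would take it as the effect in subjects who fluctuate. It would be an average over all subjects, and usually a smaller one. The protocol's background section calls fluctuation in attention and alertness one of the most characteristic features of the disease, so the label is worth getting right even on a tertiary endpoint.

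**Working it through.** **Setting the sections side by side**

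| Place | Restricted to subjects who fluctuate? |
|---|---|
| Protocol section 4, objective | No |
| Protocol section 4, endpoint | Yes |
| Protocol 10.4.3, analysis list | No |
| SAP Table 3, objective | No |
| SAP Table 3, endpoint | Yes |
| SAP 9.4.2, analysis | No; those without fluctuation enter at 0 |

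Three checks follow.

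1. *Does precedence settle it?* SAP 7.3 puts the SAP above the protocol. Here SAP Table 3 and SAP 9.4.2 disagree, so the rule does not help.
2. *Is the named endpoint delivered elsewhere?* SAP 5.8 and 9.4.2 list severity change per question and yes/no counts, all without restriction. The subgroups in SAP 7.8 do not include Baseline fluctuation. That section lets subgroups be added as the data dictate, but an addition after unblinding would be a post hoc choice.
3. *Does the model correct for it?* The MMRM in SAP 9.3.1 has baseline and baseline-by-visit terms but no treatment-by-baseline term. The treatment difference is therefore averaged over subjects at the floor.

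**Size**

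The documents give no CAF effect, SD, power or share of fluctuating subjects, so there is no CAF figure to reproduce. With f the share who fluctuate at Baseline, d the treatment difference in them, and no effect in the rest:

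all-subject difference = f × d + (1 − f) × 0 = f × d

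**Power, as an illustration only**

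From the documents: 80 randomised per arm and two-sided 5% tests. Assumed, not in the documents: d = 2 points, SD of change s = 4 in fluctuating subjects, and SD of change s0 = 0 or 4 in the others. Dropout is ignored.

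- Power = Φ(difference × √(n/2) / SD − 1.96). As a check on the formula, the UPDRS-III case (70 per arm, 4 points, SD 7.5) gives 88.4% against the stated 88%.
- Restricted analysis: n = 80f, difference 2, SD 4.
- All-subject analysis: n = 80, difference 2f, SD = √(f·s² + (1 − f)·s0² + f(1 − f)(d/2)²). The last term is a rough allowance for the gap in mean change between the two kinds of subject.

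At f = 0.5 the restricted analysis has n = 40 and 2 × √20 / 4 − 1.96 = 0.276, so power is 60.9%. The all-subject analysis with s0 = 0 has SD = √(8 + 0 + 0.25) = 2.87 and 1 × √40 / 2.87 − 1.96 = 0.24, so power is 59.6%.

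| f | Difference, restricted | Difference, all subjects | Power, restricted | Power, all subjects, s0 = 0 | Power, all subjects, s0 = 4 |
|---|---|---|---|---|---|
| 0.5 | 2.0 | 1.0 | 60.9% | 59.6% | 34.8% |
| 0.7 | 2.0 | 1.4 | 75.4% | 74.6% | 59.5% |
| 0.9 | 2.0 | 1.8 | 85.1% | 84.9% | 81.0% |

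The estimate shrinks with f. Power is almost unchanged if the non-fluctuating subjects stay at 0, and drops only as their scores vary.

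**The case against.** The best reply is that the all-subject analysis is deliberate and disclosed. Both documents' analysis sections leave CAF severity unrestricted while keeping the parallel limit for NEVHI, to subjects with visual hallucinations. The phrase in the endpoint tables may simply be left over, and deleting it would remove the conflict. This is a fair account of how the mismatch could have arisen. It does not remove it: the SAP still names one endpoint and analyses another.

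A reader might infer three stronger things that the documents do not support.

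- *That the analysis departs from the objective.* It does not. Neither objective is limited to fluctuating subjects, and an all-subject analysis answers it as worded. Only the endpoint conflicts.
- *That scoring 0 is the error.* It is not. A subject who fluctuates at Baseline and has stopped by Week 24 must score 0, or the improvement is lost. A subject with 'yes' on one item only counts as fluctuating under protocol 8.3.1.8 and properly scores 0 on the other question. The issue is confined to subjects with no fluctuation at Baseline.
- *That the effect will be understated by a known amount, with power lost.* The share f is unknown. The f × d rule also assumes no effect in the other subjects. If treatment changes new onset of fluctuation, that is real signal for the objective and the rule does not hold exactly.

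The planned yes/no analyses in all subjects will show presence of fluctuation separately from severity, so readers would not see only one blended mean. No primary or secondary conclusion depends on CAF.

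**Conclusion.** The inconsistency is real and lies inside the SAP. The severity endpoint is defined for subjects who fluctuate, the analysis covers all ITT subjects, and nothing planned reports the severity change in the named group.

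The effect on the estimate is conditional. With no treatment effect in subjects without Baseline fluctuation it is f times the effect in the others, or 50% to 90% of it for an assumed f of 0.5 to 0.9. Whether power suffers depends on how much the non-fluctuating subjects' scores vary, and it may not suffer at all.

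Priority is minor: the endpoint is tertiary, it sits outside the gated testing in SAP 7.5, and the zero rule is stated openly.

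**What to change.** Before unblinding, amend SAP 9.4.2 as follows.

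- Run the CAF severity change analysis for each question in subjects with 'yes' on either CAF item at Baseline (Visit 3), which is how protocol 8.3.1.8 defines fluctuation as present. Restricting each question to those with 'yes' on that same question would not match this definition.
- Select on the 'yes' response, not on a score above 0. SAP Table 11 scores a duration of seconds as 0, so a fluctuating subject can have severity 0.
- Keep post-baseline zeros, so that resolution counts as improvement.
- State how a Baseline response of 'Not Known' is handled.
- Show the all-subject MMRM as supportive, next to the planned all-subject yes/no CMH analyses, which cover new onset.

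The selection uses a pre-randomisation characteristic, so the comparison stays randomised. The cost is some SAP wording, one extra table and fewer subjects in the severity model. Some subjects will still start at 0 on one of the two questions, but they belong to the named population.

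The least that would remove the contradiction is to delete the restricting phrase from the endpoint tables and describe the result as an all-subject average. That would leave the effect in fluctuating subjects unreported.

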### **9.4.3. Analysis of Exploratory Efficacy Endpoints**

Exploratory endpoints include:

- For each of the five EQ-5D dimensions (Mobility, self-care, usual activities, pain/discomfort, anxiety/depression):
  - CMH RMS at Week 24
  - Using the Dichotomized values (No Problems vs Problems), a CMH general association analysis will be run at Week 24.
- Change from Baseline on EQ-5D Visual analogue score at Week 24
  - MMRM on observed data
- Change from Baseline on CSI score at Week 24
  - MMRM on observed data
- Change from Baseline on Likert scale (overall quality of sleep) at Week 24
  - MMRM on observed data
- Change from Baseline in sum of Parts D and E of the NPI at Week 24
  - MMRM on observed data

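### The CMH tests of CAF presence and EQ-5D dimension status at Week 24 leave out the same status at Baseline, which is collected; this may cost power but does not make the tests invalid.

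*SAP*

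**What the plan says.** **CAF presence (SAP 9.4.2, tertiary).** The outcome is "The number (%) of patients with CAF cognition or confusion (ie, a yes on one or the other question) at Week 24". It is analysed for each of the two questions and for either one, so there are three yes/no outcomes. The test is a "CMH test for general association (similar SAS code as for the CMH RMS but the RMS option is not needed"). The code referred to is the NEVHI sample, "Tables MMSEbase*treat*outcome / cmh rms", "where MMSEbase is the baseline randomization stratum level for the patient, NOT the actual MMSE value".

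**EQ-5D dimensions (SAP 9.4.3, exploratory).** Each of the five dimensions has two tests. The five-level response gets "CMH RMS at Week 24". For the two-level version: "Using the Dichotomized values (No Problems vs Problems), a CMH general association analysis will be run at Week 24". No stratification variable is named for either.

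**Baseline data.** The schedules (Protocol Table 2, SAP Table 2) have the CAF at Visits 1 and 3 and the EQ-5D-5L at Visit 3. The endpoints listed in Protocol section 4 are themselves changes: "Change from Baseline in CAF severity score at Week 24 for subjects with cognitive fluctuations" and "Change from Baseline on EQ-5D-5L at Week 24".

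**Use of baseline elsewhere.** The primary MMRM (SAP 9.3.1) and the ANCOVA (SAP 9.4) carry the baseline value. The NEVHI categorical test takes the shift from Baseline as its outcome.

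**The concern.** In the NEVHI analysis, baseline enters through the outcome, because the outcome is a shift. When the same code is reused for a yes/no status at Week 24, baseline drops out altogether. A subject who fluctuates at Baseline can only stay the same or lose the feature; one who does not can only stay the same or acquire it. The planned test pools the two kinds of subject within an MMSE stratum.

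If status persists over 24 weeks, baseline status explains part of the Week 24 variation, and a test that ignores it is less powerful than one that uses it. What is at stake is the sensitivity of a few lower-tier tests at about 80 subjects per arm.

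**Working it through.** **1. The plan's own figures.** The documents give no power, prevalence or correlation for these CMH tests. The stated power for the primary endpoint reproduces: 4 / (7.5 × √(2/70)) − 1.96 = 3.155 − 1.960 = 1.195, and Φ(1.195) = 88.4% (stated: 88%).

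**2. Inputs.** From the documents: two-sided 5%, 1:1:1 allocation, about 80 per arm (240/3), 70 per arm as the lower figure used for UPDRS-III sizing, and three MMSE strata. Assumed: baseline prevalence equal to the placebo Week 24 rate; Week 24 rates of 50% vs 30%, 60% vs 40%, 70% vs 50%, 80% vs 60% or 85% vs 70%; Baseline to Week 24 correlation φ from 0 to 0.6 in both arms; equal-sized, non-prognostic MMSE strata.

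**3. Model.** With baseline prevalence b and Week 24 rate p in an arm, let c = φ√[b(1−b)p(1−p)]. Then P(yes | baseline yes) = p + c/b and P(yes | baseline no) = p − c/(1−b). Example, placebo with b = p = 0.7 and φ = 0.5: c = 0.5 × 0.21 = 0.105, giving 0.7 + 0.105/0.7 = 0.85 and 0.7 − 0.105/0.3 = 0.35.

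**4. Test.** For one dose against placebo, over strata h, with a = active subjects with a yes, n₁ and n₀ = subjects per arm, m₁ and m₀ = subjects with and without a yes, and n = stratum total:

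X² = [Σ(a − n₁m₁/n)]² / Σ[n₁n₀m₁m₀ / (n²(n−1))], compared with 3.84.

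This was run with 3 strata (MMSE) and with 6 (MMSE × baseline status), 10,000 simulated trials per setting.

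**5. Results.** The first two columns of power are for 80 per arm, 70% vs 50%. The last column is the range over all five rate pairs at 70 and 80 per arm.

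| φ | MMSE only | MMSE × baseline | Change, all settings (points) |
|---|---|---|---|
| 0 | 73.9% | 73.1% | −1.2 to −0.4 |
| 0.2 | 73.1% | 74.0% | +0.6 to +1.2 |
| 0.3 | 73.6% | 77.1% | +2.5 to +3.5 |
| 0.4 | 74.0% | 80.3% | +5.7 to +6.9 |
| 0.5 | 72.2% | 84.2% | +9.9 to +12.0 |
| 0.6 | 73.1% | 89.8% | +13.4 to +18.1 |

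With 50% in both arms, the rejection rate was 4.6% to 5.4% across both versions.

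**6. Hand check.** Adjusting for a covariate with correlation φ acts roughly like enlarging the sample to n/(1 − φ²). At φ = 0.5 that is 80/0.75 = 106.7 per arm. Power is Φ[(0.2 − 1.96√(2×0.6×0.4/106.7)) / √(0.46/106.7)] = Φ(1.04) = 85%, close to the simulated 84.2%. At φ = 0 the same formula gives 73.7%.

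**7. A different effect model.** Here the drug acts only in baseline-positive subjects (70 per arm, 20,000 trials). Settings are baseline prevalence; placebo vs active rate in baseline-positives; common rate in baseline-negatives.

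| Setting | Placebo φ | MMSE only | MMSE × baseline |
|---|---|---|---|
| 75%; 85 vs 65%; 20% | 0.61 | 44% | 55% |
| 60%; 85 vs 65%; 20% | 0.65 | 29% | 38% |
| 75%; 80 vs 60%; 30% | 0.46 | 44% | 49% |
| 80%; 80 vs 60%; 40% | 0.36 | 50% | 53% |
| 75%; 70 vs 50%; 40% | 0.27 | 43% | 44% |
| 90%; 80 vs 60%; 40% | 0.28 | 62% | 64% |

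The direction agrees in all six settings, with gains of about 1 to 11 points.

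**The case against.** Five points weigh against this, and most of them stand.

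- **The tests are valid.** A reader might infer that chance imbalance in baseline prevalence biases the Week 24 comparison. It does not: under randomisation that imbalance is sampling variation which the p-value already covers, and the simulated type I error is about 5% either way.
- **No controlled claim depends on them.** SAP 7.5 covers the primary and secondary endpoints only.
- **Baseline is already used for these instruments.** CAF severity is analysed as change from Baseline by MMRM, with subjects without fluctuation scored 0 and kept in. The EQ-5D visual analogue score is also analysed as change. This lowers the stakes, but severity and presence are different questions, and the visual analogue score does not replace the dimension tests.
- **The gain may be negligible.** At a correlation of 0.2 or less it is about a point or nothing. Persistence is plausible, since fluctuating cognition is a core diagnostic feature in the inclusion criteria, but the documents do not quantify it.
- **The text is not fully explicit.** The code is labelled as a sample, and MMSE-only stratification for the EQ-5D is inferred from it. For the EQ-5D the documented gap is that no strata are stated.

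A reader might also infer that every other efficacy model adjusts for baseline. CIBIC+ does not (SAP 9.4.1), though it is itself a rating of change.

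**Conclusion.** The point holds as a matter of efficiency, at minor priority. The planned CMH tests ignore a collected baseline value that probably predicts the outcome. For 70 to 80 per arm, the change in power from using it runs from about −1 point at zero correlation to +10 to +12 points at 0.5, and more above that. Where this trial falls in that range cannot be told from the documents. Quoting only the largest gains would rest on assumed persistence that they do not support.

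The simulations cover yes/no outcomes. For the five-level EQ-5D test the same reasoning applies, but no gain was calculated.

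**What to change.** Before unblinding:

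- For the three CAF yes/no outcomes and the five EQ-5D dichotomies, use `Tables MMSEbase*baseline_status*treat*outcome / cmh`, where `baseline_status` is the same variable at Baseline (six strata).
- For the five-level EQ-5D CMH RMS tests, add baseline problem/no problem as a stratum.
- Write out the EQ-5D strata in SAP 9.4.3.
- State that each dose is compared with placebo separately, in line with SAP 7.5; the sample code does not limit the treatment variable to two arms.
- Say how a missing or Not Known baseline CAF answer is classified, so that those subjects are not dropped by default.

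Logistic regression with baseline status and MMSE stratum as covariates would be an acceptable alternative.

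The cost is one more variable in existing code and no new data. A few strata will be sparse and contribute little. If baseline status carries no information, the loss is about 1 point of power.
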